## 7. STATISTICAL METHODOLOGY AND STATISTICAL ANALYSES

### 7.1 STATISTICAL METHODS

Statistical analysis will be done using statistical software R ([www.r-project.org](http://www.r-project.org)).

For the statistical analysis is planned to use descriptive statistics, confidence intervals for difference in proportion (See section 8 [1]), mixed-effect model, two sample t-test, one-sample t-test, Wilcoxon test, Mann-Whitney test, Fisher exact test, Shapiro-Wilk test and permutation tests (See section 8 [2]).

### 7.2 STATISTICAL ANALYSES

#### 7.2.1 Disposition of Subjects

Disposition of all subjects (enrolled, randomized, discontinued) in analyzed population will be presented.

#### 7.2.2 Demographic and baseline characteristics

This data will be presented for ITT population by treatments group at baseline (Day 1).

Continuous data will be presented with number of non-missing values, mean, standard deviation, median, minimal and maximal values.

Nominal data will be presented with absolute and relative (percent) frequencies.

Between groups continuous data will be compared using unpaired Student's *t*-test (for normally distributed data) or Mann-Whitney test (for free distribution data). Between groups binominal data will be compared using Fisher exact test, for categorical data Mann-Whitney test will be used.

### 7.2.3 Primary Efficacy Analysis

According to the Guideline EMA/EWP-482 (Superiority-non-inferiority and switching), in non-inferiority study primary analysis must be performed on Per-Protocol population (see chapter IV.1.4 Choice of analysis set of the guideline).

The main efficacy analysis population is defined as Per-Protocol (PP).

Study statistical testing hypothesis is expressed as:

H0: Lower bound of the 97.5% one-sided CI ( $p_1 - p_2$ )  $\leq -20\%$  => Non-inferiority rejected

H1: Lower bound of the 97.5% one-sided CI ( $p_1 - p_2$ )  $> -20\%$  => Non-inferiority accepted

The primary objective is to demonstrate the "non-inferiority" of Levopront® comparing to Libexin® with regards to the primary endpoint. For this purpose, the one-sided 97.5% Confidence Interval (CI) will be calculated for the two proportions difference — the rate of patients who responded to treatment (**cough absents**, when score is 0 or 1 at "six-point cough scale" vs. **cough presents**, when score is  $\geq 2$  at "six-point cough score") by Day 8 in the study treatment group and in the control group with a non-inferiority margin of  $\delta = 20\%$ . The null hypothesis (H0) that in the study treatment group the rate of treatment responders is less than in the control group, will be declined if the lower bound of the 97.5% one-sided CI for the two proportions difference is located to the right of the **-0.20**, with the final conclusion of non-inferiority of Levopront® versus Libexin®.

The proportion difference will be calculated using **Newcombes Hybrid Score** method (1998). See 8 [1].

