9.7 Efficacy Analysis

9.7.1 Primary Efficacy Endpoint

Primary endpoint: -The main efficacy analysis population includes all randomized patients completing treatment with the study drug (PP population)

Study statistical testing hypothesis will be expressed as:

H₀: Lower bound of the 97.5% one-sided CI ($p_1 - p_2$) \leq -20% → Non-inferiority rejected

H₁: Lower bound of the 97.5% one-sided CI ($p_1 - p_2$) $>$ -20% → Non-inferiority accepted

The primary objective is to demonstrate the "non-inferiority" of Levopront® comparing to Libexin® with regards to the primary endpoint. For this purpose, the one-sided 97.5% CI will be calculated for the two proportions difference — the rate of patients who responded to treatment by Day 8 in the study treatment group and in the control group with a non-inferiority margin of $\delta = 20\%$. The null hypothesis (H₀) that in the study treatment group the rate of treatment responders is less than in the control group, will be declined if the lower bound of the 97.5%

one-sided CI for the two proportions difference is located to the right of the -0.20, with the final conclusion of non-inferiority of Levopront® versus Libexin®.

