9.9 Procedures of Account of Missing, Non-Analyzable and Doubtful Data

Missing data will not be substituted. For analysis of efficacy end points the last observation carried forward method (LOCF) will be used. For sensitivity assessment will be used sensitivity analyses: first the patients with missing data as failure will be analysed and second the patients without substitution of missing data

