### **5. ANALYSIS SETS**

#### **5.1 PER PROTOCOL POPULATION**

Per-protocol population includes all randomized patients completing treatment with the study drug, having primary efficacy analysis assessment done and considered to be compliant. Patients without serious deviations from protocol during the study will be considered compliant. The key protocol deviations will be determined before the date of database lock. PP population is the primary population for the primary endpoint (Non-inferiority) analysis

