#### **5.2 INTENT-TO-TREAT POPULATION**

The population of patients is based on the initial treatment assignment and not on the treatment eventually received (ITT).

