**Table 9.9 Primary efficacy. Daytime cough resolution.**

ITT analysis set. N = xx

	Levopront® (Test) n (%) N = XX	Libexin® (Control) n (%) N = XX
Daytime cough resolution		
Ongoing (≥2)	xx (xx.x%)	xx (xx.x%)
Resolved (<2)	xx (xx.x%)	xx (xx.x%)
Test – Control (resolved)	xx (xx.x%) 97.5% CI [xx.x%; --]	

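### Non-inferiority is decided on the per-protocol bound alone; the plan gives no consequence if the ITT bound fails

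*SAP*

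**What the plan says.** The SAP names the deciding population twice: "PP population is the primary population for the primary endpoint (Non-inferiority) analysis" (5.1) and "The main efficacy analysis population is defined as Per-Protocol (PP") (7.2.3). Protocol 9.7.1 agrees: "The main efficacy analysis population includes all randomized patients completing treatment with the study drug (PP population"). Both documents attach the acceptance rule to a single interval: the lower limit of the one-sided 97.5% CI against -0.20, by Newcombe's hybrid score method in SAP 7.2.3.

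Membership of the deciding set depends on what happens after randomisation: "Per-protocol population includes all randomized patients completing treatment with the study drug, having primary efficacy analysis assessment done and considered to be compliant" (SAP 5.1). Protocol 9.4.1 leaves the detail of key deviations to the SAP, but the SAP does not list them: "The key protocol deviations will be determined before the date of database lock".

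ITT is defined by assignment: "The population of patients is based on the initial treatment assignment and not on the treatment eventually received (ITT"). The SAP text uses it for baseline data (7.2.2) and secondary efficacy (7.2.4). For the primary endpoint it appears only as a table shell, "Table 9.9 Primary efficacy. Daytime cough resolution", which prints the same 97.5% bound with no rule attached.

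On missing data, protocol 9.9 names LOCF and two sensitivity analyses, of which "first the patients with missing data as failure will be analysed". SAP 6.1 plans no replacement of missing efficacy values. Neither links any of this to the non-inferiority decision.

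**The concern.** A comparison restricted to compliant completers is not protected by randomisation. The trial is open-label, and several exits listed in protocol 6.13 can go with treatment failure: lower respiratory infection, adverse events, non-compliance and use of prohibited drugs, which under protocol 5.7 include other antitussives. If more failures are removed from the Levopront arm than from the Libexin arm, the PP difference moves towards Levopront.

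The ITT analysis could expose this, but the plan does not say what follows if the two sets disagree. Read literally, the PP result stands. With no rule set in advance, a conflict would be interpreted after the results are known.

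**Working it through.** **1. The plan's own sample size.** Inputs from protocol 9.2: z = 1.96 and 0.84, 70% in both arms, margin 20 points, early discontinuation up to 10%.

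n = (1.96 + 0.84)² × (0.70×0.30 + 0.70×0.30) / 0.20² = 7.84 × 0.42 / 0.04 = 82.3 per arm. Then 82.3 / 0.9 = 91.5, so 92 per arm and 184 in total. The stated figure reproduces.

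**2. The bound.** Newcombe lower limit: L = (pT - pC) - √[(pT - lT)² + (uC - pC)²]. Here T is Levopront, C is Libexin, lT is the lower Wilson limit for T and uC the upper Wilson limit for C, both at z = 1.96.

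**3. A constructed example in which the sets disagree.** All losses are Levopront failures: 9 of 92 (9.8% of that arm, none from Libexin).
- ITT, 54/92 v 64/92: pT = 0.587, lT = 0.485, pC = 0.696, uC = 0.780. Difference -10.9 points; L = -0.109 - √(0.102² + 0.085²) = -24.1 points. Fails.
- PP, 54/83 v 64/92: pT = 0.651, lT = 0.543. Difference -4.5 points; L = -0.045 - √(0.107² + 0.085²) = -18.2 points. Passes.

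Under the written rule this trial is declared non-inferior.

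**4. Error rate of the PP-only rule.** True rates are set at the margin (50% v 70%), with 92 randomised per arm and trials simulated with the Newcombe bound. The fractions of failures leaving are assumptions. If a fraction f of failures leaves an arm with true rate p, the expected PP rate is p / [1 - f(1 - p)]. With f = 0.2, for example, Levopront gives 0.5/0.9 = 55.6% and Libexin 0.7/0.94 = 74.5%.

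| Failures leaving, Levopront v Libexin | Share of arm lost | Expected PP difference | False acceptance, PP only |
|---|---|---|---|
| 10% v 20% | 5% v 6% | 52.6 - 74.5 = -21.8 | 1.5% |
| none | 0 v 0 | -20.0 | 2.6% |
| 20% v 20% | 10% v 6% | 55.6 - 74.5 = -18.9 | 3.9% |
| 20% v 10% | 10% v 3% | 55.6 - 72.2 = -16.6 | 7.4% |
| 20% v 0% | 10% v 0% | 55.6 - 70.0 = -14.4 | 12.6% (12.7% in a repeat run) |

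(Differences are computed before rounding.) Two further cases: if 10% of each arm leaves and all are failures, the rate is 1.3%; if 10% of each arm leaves regardless of outcome, it is 2.8%.

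**5. Requiring both sets.** If ITT uses the observed outcomes of everyone randomised, joint false acceptance is 2.6% or less in these scenarios. If every leaver is counted as a failure, that protection can be lost. When 10% of Libexin responders leave, the joint rule accepts falsely in 5.5% of trials; when 20% of Levopront failures leave as well, in 14.3%. Counting missing Libexin outcomes as failures lowers the control rate and so favours non-inferiority.

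**6. Power at 70% in both arms, 10% random exclusion per arm.** PP alone 81.8%; both sets with outcomes observed 80.2%; both sets with the excluded counted as failures 77.2%.

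**The case against.** PP as the primary set is a deliberate choice, stated consistently in both documents and referenced in SAP 7.2.3 to a named guideline. That stands, and nothing here asks for PP to be replaced. The citation is given for the choice of PP; the SAP draws from it no rule for a conflicting ITT result.

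A PP/ITT conflict would also not be hidden. Table 9.9 reports the ITT bound under a primary-efficacy title, and protocol 9.9 pre-specifies a missing = failure analysis. That also stands: the gap is an unstated consequence, not an absent analysis.

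Three stronger readings are tempting and not supported:
- *That the PP-only rule necessarily inflates the error.* The direction depends on which failures leave. Some patterns lower the error (1.5%, 1.3%), and loss unrelated to outcome barely moves it (2.8%). The documents give no figure by arm or outcome, so the higher rates show what is possible, not what is expected.
- *That exclusions from the PP set cannot be traced.* Table 9.1 has a row for completing per protocol and lists discontinuation reasons by arm, and Table 9.8 gives the PP N. Only a labelled PP-set row is missing.
- *That adding ITT with missing = failure controls the error in every case.* Step 5 shows that it does not when Libexin responders are missing.

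**Conclusion.** The point holds as a gap in the decision rule: the PP bound alone decides, and the plan does not say what an ITT failure would mean. At the margin, PP-only false acceptance runs from 1.5% to about 12.6% across the tabulated loss patterns, against 2.6% with no loss. Inflation of any size requires loss that favours Levopront. An equal fraction of failures leaving both arms is enough for a small rise (3.9%), because under a true deficit Levopront has more failures to lose. The open-label design and a deviation list settled only before database lock make selective loss possible, but the documents do not show that it is likely. This should be fixed. It does not invalidate the choice of PP as primary.

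**What to change.** Keep PP as primary. In protocol 9.7.1 and SAP 7.2.3, state that non-inferiority is concluded only if the one-sided 97.5% Newcombe lower bound exceeds -20 points in both the PP set and the ITT set (all randomised, as assigned), and that it is not shown if the two disagree.

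For ITT:
- Use the observed Day 8 score, or the early-termination-visit score that protocol 7.5 already seeks, whatever the patient's PP status.
- Count a patient as a non-responder only if no such score exists.
- Add a sensitivity analysis that varies the missing Libexin outcomes, since missing = failure in the control arm favours non-inferiority.
- Reconcile SAP 6.1 (no replacement) with protocol 9.9 (LOCF and missing = failure). Under SAP 6.1 as written, patients without a Day 8 score could drop out of Table 9.9 too.

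State the joint power. At 70% in both arms with 10% random exclusion it is about 80% if outcomes are observed and about 77% if all the excluded count as failures, against about 82% for PP alone. The cost is therefore protocol and SAP wording plus roughly 2 to 5 points of power. If most leavers have no score, 184 patients would fall about 3 points short of the 80% target.

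Minor: add a labelled PP-set row to Table 9.1.

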### 7.2.4 Secondary Efficacy Analyses

Secondary efficacy analysis will be performed on the ITT population.

#### 7.2.4.1 Nighttime cough resolution rate by Day 8

Nighttime cough symptoms will be classified as **Absent** (<2 at six-point cough scale) or **Present** ( $\geq 2$  at six-point cough scale). For such derivation treatment groups will be compared using the Fisher exact test.

#### 7.2.4.2 Daytime and nighttime cough symptoms resolution by Day 4

Daytime and Nighttime cough symptoms will be classified as **Absent** (<2 at six-point cough scale) or **Present** ( $\geq 2$  at six-point cough scale). Resolution Daytime (<2 at scale) and Nighttime (<2 at scale) symptoms at Day 4 will be described by treatment groups. Treatment groups will be compared using the Fisher exact test.

#### 7.2.4.3 Change in severity and frequency of daytime and nighttime cough on Day 4 and Day 8 from baseline on Day 1

Scores from the six-point cough scale will be described by visits and treatment groups together with changes from baseline (Day 1). Within group change will be tested using paired t-test (normal data) or Wilcoxon sign test (violation of normality), between groups test – two sample t-test (normal data) or Mann-Whitney test (violation of normality). Test for normality – Shapiro-Wilk.

Treatment groups will be also compared at baseline (Day 1). In case of significant difference (statistically) in scores/values at baseline a mixed-effect model will be

discussed.

Parameter dynamics also will be presented with graphics (see Figure 9.1).

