The patients will take the etiotropic and pathogenetic therapy of the main disease.

Patients will not take antibiotics, mucolytics and expectorants, antiviral drugs (except Arbidol®); combined "anti-commoncold" drugs; antihistamines; drugs that have a sedative effect and reinforcing the depressive effect on the central nervous system, as well as other cough suppressants, except for the study drugs.

Duration of the study:

Each patient's study participation will last for approximately 10 days and include the following stages: screening and randomization (Day 1), study treatment period (7 days), follow-up period (2 days).

The first part of the study started on 09 November 2016 (First Visit First Patient) and it has been completed on 27 April 2017 (Last Visit Last Patient). For the second part of the study, the start of patient enrollment is expected in November, 2017 and the completion of the study visits in February 2018.

Efficacy Endpoints

The primary efficacy endpoint is the rate of patients responded to the treatment — daytime cough symptoms resolution — by Day 8. The daytime cough symptoms resolution corresponds to 0 or 1 point according to the "Six-point daytime and nighttime cough assessment scale".

The secondary efficacy endpoints include:

- Rate of patients responded to the treatment — nighttime cough symptoms resolution — by Day 8.
- Rate of responders with daytime and nighttime cough symptoms resolution according to the "Six-point daytime and nighttime cough assessment scale" by Day 4.
- Mean change in cough severity and frequency according to the "Six-point daytime and nighttime cough assessment scale" on Day 4 and 8 from baseline on Day 1.
- Mean change in cough intensity according to the visual-analogue scale on Day 4 and 8 from baseline on Day 1.
- Mean change of FEV1 on Day 8 from baseline on Day 1.

Safety assessment

The safety will be evaluated based on the rate of AE and SAE of different severity according to the data from subjective complaints, laboratory testing results, physical examination, vital signs and spirometry.

Statistic methods:

Efficacy analysis

Per-protocol population analysis (PP) includes all randomized patients completing treatment with the study drug, having primary efficacy analysis assessment done and considered to be compliant. PP population will be the primary population for efficacy analysis²².

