4.2 Inclusion Criteria

Subjects should meet the following inclusion criteria to be included into this clinical trial:

1. Signed Informed Consent Form
2. Male or female aged from 18 to 65 (inclusive)
3. Dry non-productive cough as a symptom of acute upper respiratory infection (IDC codes J00-J06)
4. Daytime cough symptom score ≥ 3 points according to the "Six-point daytime and nighttime cough assessment scale"
5. Pre-bronchodilator FEV1 $\geq 70\%$ of the predicted values, post-bronchodilator FEV1 increase of $\leq 12\%$ or ≤ 200 ml compared to the baseline, FEV1/FVC (Tiffeneau index) ≥ 0.7
6. Patient's consent to follow the protocol procedures, including the completion of the patient's diary
7. Patient's consent to use the adequate contraception methods throughout the study period. The adequate birth control methods are as follows:
 - Oral or transdermal contraceptives
 - Condoms or diaphragms (barrier method) with spermicide
 - Intrauterine contraceptive devices

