
Side effects
 
Allergic Reactions
 
Rare: - skin rash;
 
- Angioedema
 
Gastrointestinal tract disorders
 
- Rare: - dry mouth or throat;
 
- Anesthesia (temporary numbness and loss of sensitivity) of oral mucosa;
 
- Less than in 10% cases:
 
- Gastric pain;
 
- Disposition to constipations;
 
- Nausea
 
Nervous system disorders (at high doses)
 
- Mild sedative effect;
	
Side effects
 
Allergic Reactions
 
Rare: - skin rash;
 
- Angioedema
 
Frequency unknown: bronchospasm
 
Gastrointestinal tract disorders
 
- Rare: - dry mouth or throat;
 
- Anesthesia (temporary numbness and loss of sensitivity) of oral mucosa;
 
- Less than in 10% cases:
 
- Gastric pain;
 
- Disposition to constipations;
 
- Nausea
 
Nervous system disorders (at high doses)
 
Mild sedative effect

Appendix 2
Six-point daytime and nighttime cough assessment scale

Score	Daytime cough	Score	Nighttime cough
0	No cough	0	No cough
1	Single cough impulses	1	Cough does not interfere with sleep
2	Rare cough at daytime	2	Cough interrupting sleep not more than 2 times in a night
3	Frequent cough not interfering with daily activities	3	Cough interrupting sleep over 2 times in a night
4	Frequent cough impairing daily activities	4	Frequent sleep interruption caused by cough
5	Severe cough, impossible to maintain daily activities	5	Cough precluding sleep

Appendix 3

Visual analog scale

Please mark on the scale below your cough intensity.

Cough Intensity

no cough

Heavy, Severe cough

NB: Please use only VAS provided by IPHARMA and avoid to perform any copy of the form.

In case, for any reason, you need to perform a reproduction of the form, after any reproduction verify the length of the VAS: the line must be 100 mm

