## 9. TABLE EXAMPLES

### 9.1 DEMOGRAPHICS AND BASELINE

Table 9.1 Disposition

	Levopront ® (T) n (%)	Libexin ® (C) n (%)
Enrolled subject	xx	xx
Randomized subjects	xx (xx.x%)	xx (xx.x%)
ITT Analysis Set	xx (xx.x%)	xx (xx.x%)
Safety Analysis Set	xx (xx.x%)	xx (xx.x%)
Completed Study per protocol	xx (xx.x%)	xx (xx.x%)
Discontinued prematurely	xx (xx.x%)	xx (xx.x%)
Adverse Event	xx (xx.x%)	xx (xx.x%)
Death	xx (xx.x%)	xx (xx.x%)
Infection of lower respiratory tract	xx (xx.x%)	xx (xx.x%)
Lost to follow-up	xx (xx.x%)	xx (xx.x%)
Consent withdrawn	xx (xx.x%)	xx (xx.x%)
Investigator decision	xx (xx.x%)	xx (xx.x%)
Protocol violation, including non-compliance	xx (xx.x%)	xx (xx.x%)
Protocol entry criteria not met	xx (xx.x%)	xx (xx.x%)
Study is stopped by Sponsor decision	xx (xx.x%)	xx (xx.x%)
Study is stopped by regulatory authorities / ethics committee	xx (xx.x%)	xx (xx.x%)
Other	xx (xx.x%)	xx (xx.x%)
Pregnancy	xx (xx.x%)	xx (xx.x%)

Table 9.2 Demographic and other baseline characteristics.  
ITT analysis set. Screening (baseline). N = xx

Parameter	Levopront ® (T) n (%)	Libexin ® (C) n (%)	p-value
Age (years)			
N	xx	xx	0.xxx
Mean (SD)	xx.x (xx.x)	xx.x (xx.x)	
Median	xx.x	xx.x	
Min - Max	xx.x – xx.x	xx.x – xx.x	
Gender			
Male	xx (xx.x%)	xx (xx.x%)	0.xxx
Female	xx (xx.x%)	xx (xx.x%)	
No data 	xx (xx.x%)	xx (xx.x%)	
Race			
Caucasian	xx (xx.x%)	xx (xx.x%)	
Other	xx (xx.x%)	xx (xx.x%)	
No data 	xx (xx.x%)	xx (xx.x%)	
Height (cm)			
N	xx	xx	---
Mean (SD)	xx.x (xx.x)	xx.x (xx.x)	
Median	xx.x	xx.x	
Min - Max	xx.x – xx.x	xx.x – xx.x	
Weight (kg)			
N	xx	xx	---
Mean (SD)	xx.x (xx.x)	xx.x (xx.x)	
Median	xx.x	xx.x	
Min – Max	xx.x – xx.x	xx.x – xx.x	
BMI (kg/m^2)			
N	xx	xx	0.xxx
Mean (SD)	xx.x (xx.x)	xx.x (xx.x)	
Median	xx.x	xx.x	
Min - Max	xx.x – xx.x	xx.x – xx.x	
Duration of the acute upper respiratory infection (days)			

 Tables in the report may differ from this templates but meaning and information presented should be kept

 if any

 if any

Parameter	Levopront® (T) n (%)	Libexin® (C) n (%)	p-value
N	xx	xx	0.xxx
Mean (SD)	xx.x (xx.x)	xx.x (xx.x)	
Median	xx.x	xx.x	
Min - Max	xx.x – xx.x	xx.x – xx.x	
Duration of dry non-productive cough (days)			
N	xx	xx	0.xxx
Mean (SD)	xx.x (xx.x)	xx.x (xx.x)	
Median	xx.x	xx.x	
Min - Max	xx.x – xx.x	xx.x – xx.x	

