**Table 9.10 Secondary efficacy. Nighttime cough resolution.**

ITT population set. N = xx

	Levopront® (Test) n (%) N = XX	Libexin® (Control) n (%) N = XX
Nighttime cough resolution		
Ongoing (≥2)	xx (xx.x%)	xx (xx.x%)
Resolved (<2)	xx (xx.x%)	xx (xx.x%)
p-value (Fisher)	0.xxx	

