**Table 9.11 Secondary efficacy. Daytime and Nighttime cough resolution.**

ITT population set. N = xx

	Levopront® (Test) n (%) N = XX	Libexin® (Control) n (%) N = XX
Daytime & Nighttime cough resolution		
Ongoing (≥2)	xx (xx.x%)	xx (xx.x%)
Resolved (<2)	xx (xx.x%)	xx (xx.x%)
p-value (Fisher)	0.xxx	

**Table 9.12 Change in severity and frequency of daytime and nighttime cough on Day 4 and Day 8 from baseline on Day 1. ITT population. N = xx**

	Day 1 (baseline)	Day 4	Change at Day 4	Day 8	Change at Day 8
Levopront®					
Daytime cough					
N	xx	xx	xx	xx	xx
Mean (SD)	xx.x (xx.x)	xx.x (xx.x)	xx.x (xx.x)	xx.x (xx.x)	xx.x (xx.x)
Median	xx.x	xx.x	xx.x	xx.x	xx.x
Min – Max	xx.x – xx.x	xx.x – xx.x	xx.x – xx.x	xx.x – xx.x	xx.x – xx.x
p-change			0.xxx		0.xxx
Libexin®					
Daytime cough					
N	xx	xx	xx	xx	xx
Mean (SD)	xx.x (xx.x)	xx.x (xx.x)	xx.x (xx.x)	xx.x (xx.x)	xx.x (xx.x)
Median	xx.x	xx.x	xx.x	xx.x	xx.x
Min - Max	xx.x – xx.x	xx.x – xx.x	xx.x – xx.x	xx.x – xx.x	xx.x – xx.x
p-change			0.xxx		0.xxx
p-between	0.xxx		0.xxx		0.xxx
Levopront®					
Nighttime cough					
N	xx	xx	xx	xx	xx
Mean (SD)	xx.x (xx.x)	xx.x (xx.x)	xx.x (xx.x)	xx.x (xx.x)	xx.x (xx.x)
Median	xx.x	xx.x	xx.x	xx.x	xx.x
Min - Max	xx.x – xx.x	xx.x – xx.x	xx.x – xx.x	xx.x – xx.x	xx.x – xx.x
p-change			0.xxx		0.xxx
Libexin®					

	Day 1 (baseline)	Day 4	Change at Day 4	Day 8	Change at Day 8
Nighttime cough					
N	xx	xx	xx	xx	xx
Mean (SD)	xx.x (xx.x)	xx.x (xx.x)	xx.x (xx.x)	xx.x (xx.x)	xx.x (xx.x)
Median	xx.x	xx.x	xx.x	xx.x	xx.x
Min - Max	xx.x - xx.x	xx.x - xx.x	xx.x - xx.x	xx.x - xx.x	xx.x - xx.x
p-change			0.xxx		0.xxx
p-between	0.xxx		0.xxx		0.xxx

Figure 9.1 Graphics example

Graphics example

[figure not shown]

Table 9.13 Cough intensity change according to the visual-analogue scale on Day 4 and Day 8 from baseline on Day 1. ITT population. N = xx

	Day 1 (baseline)	Day 4	Change at Day 4	Day 8	Change at Day 8
Levopront®					
Cough intensity. VAS					
N	xx	xx	xx	xx	xx
Mean (SD)	xx.x (xx.x)	xx.x (xx.x)	xx.x (xx.x)	xx.x (xx.x)	xx.x (xx.x)
Median	xx.x	xx.x	xx.x	xx.x	xx.x
Min - Max	xx.x - xx.x	xx.x - xx.x	xx.x - xx.x	xx.x - xx.x	xx.x - xx.x
p-change			0.xxx		0.xxx
Libexin®					

	Day 1 (baseline)	Day 4	Change at Day 4	Day 8	Change at Day 8
Cough intensity. VAS					
N	xx	xx	xx	xx	xx
Mean (SD)	xx.x (xx.x)	xx.x (xx.x)	xx.x (xx.x)	xx.x (xx.x)	xx.x (xx.x)
Median	xx.x	xx.x	xx.x	xx.x	xx.x

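### SAP 7.2.4.1 and Table 9.10 count patients whose night score was already below 2 on Day 1 as resolved at Day 8, so the nighttime response rate can be overstated

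*SAP*

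**What the plan says.** The protocol synopsis, under Efficacy Endpoints, lists as a secondary endpoint: "Rate of patients responded to the treatment — nighttime cough symptoms resolution — by Day 8". The synopsis and section 2.1 define resolution as a score of 0 or 1, but for daytime cough only.

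The only cough-score entry criterion, in protocol 4.2, is "Daytime cough symptom score ≥ 3 points according to the" six-point scale. Appendix 2 scores day and night separately; night score 0 is no cough and night score 1 is "Cough does not interfere with sleep". A patient with a daytime score of 3 and a night score of 0 or 1 is eligible.

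SAP 7.2.4 places secondary efficacy on the ITT population. SAP 7.2.4.1 states: "Nighttime cough symptoms will be classified as Absent (<2 at six-point cough scale"); a score of 2 or more is present. The arms are compared by Fisher's exact test, and nothing refers to the Day 1 night score. The shell headed "Secondary efficacy. Nighttime cough resolution" has two rows, ongoing (2 or more) and resolved (below 2), and a Fisher p-value. A footnote to SAP section 9 says: "Tables in the report may differ from this templates but meaning and information presented should be kept".

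For the scores themselves, SAP 7.2.4.3 is baseline-aware. It analyses change from Day 1, compares the arms at baseline, and says a mixed-effect model will be discussed if the baselines differ significantly.

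**The concern.** For daytime cough the 0-or-1 rule works, because everyone enters at 3 or more and has something to resolve. The SAP applies the same cut-off at night, where entry gives no such assurance. A patient below 2 on both Day 1 and Day 8 had no night cough of 2 or more to lose, yet is counted as resolved.

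Two things are at stake. The absolute rate in each arm can look better than it was among patients who had night cough. The comparison between arms is diluted by patients who contribute no information about resolution. In a trial meant to show that the test drug is not worse, pulling the arms together is not conservative.

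A reader could not undo this from the planned output. Table 9.2 has no cough score, and Table 9.12 gives N, mean, SD, median and range but not the number below 2 on Day 1.

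A second, separate gap concerns the same tables. Protocol 9.7.2 calls for 95% CIs for secondary endpoints, while SAP 7.2.4.1, 7.2.4.2 and Tables 9.10 and 9.11 provide only a Fisher p-value. A non-significant p-value does not show similarity; an interval shows which differences remain possible.

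**Working it through.** **The plan's own figure.** The documents give no rate or sample size for the nighttime endpoint. The nearest anchor is the primary daytime calculation in protocol 9.2: (1.96 + 0.84)² × (0.7 × 0.3 + 0.7 × 0.3) / 0.20² = 82.3 per arm; 82.3 / 0.9 = 91.5, rounded up to 92. This reproduces. From it I take N = 92 per arm and the 70% rate, which is a daytime rate.

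**Notation.**
- f: share of patients below 2 at night on Day 1. Not in the documents; assumed 10%, 30%, 50%.
- s: probability that such a patient is below 2 on Day 8. Not in the documents; assumed 100%, 90%, 70%.
- q: resolution rate among patients at 2 or more on Day 1. Assumed 70%, borrowed from daytime.

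**Reported rate.** Rate = f·s + (1 − f)·q, which exceeds q by f·(s − q). There is overstatement only if f > 0 and s > q.

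| q = 70% | f = 10% | f = 30% | f = 50% |
|---|---|---|---|
| s = 100% | 73% | 79% | 85% |
| s = 90% | 72% | 76% | 80% |
| s = 70% | 70% | 70% | 70% |

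**Dilution.** With f and s equal across arms, the expected difference is (1 − f) times the difference among patients with night cough. If q were 50% vs 70%, the 20 points would appear as 18, 14 or 10 points at f = 10%, 30% or 50%.

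**Chance imbalance.** Randomisation is unstratified (protocol 9.3).
- With f = 30% vs 20%, q = 70% in both arms and s = 100%: 0.30 + 0.70 × 0.70 = 79% against 0.20 + 0.80 × 0.70 = 76%, a spurious 3 points.
- At f = 30% in both arms, the SD of the chance difference in f is √(2 × 0.3 × 0.7 / 92) = 6.8 points. Multiplied by s − q = 0.30, this moves the difference by an SD of 2.0 points.
- The total SE, √(2 × 0.79 × 0.21 / 92) = 6.0 points, already includes that variation.

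**Fisher's test, two-sided 5%, exact enumeration, s = 100%.** With q = 70% in both arms, the type I error for all ITT is 3.4%, 3.3% and 3.1% at f = 10%, 30% and 50%, so the test remains valid. Power for an assumed 50% vs 70%:

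| f | All ITT, 92 per arm | Day 1 night score ≥ 2 only |
|---|---|---|
| 10% | 67.8% | 69.9% (83 per arm) |
| 30% | 49.9% | 58.7% (64 per arm) |

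**Worked example, f = 30%.** In each arm 28 patients start and stay below 2. Of the other 64, 32 resolve on Levopront and 45 on Libexin.
- All ITT: 60/92 vs 73/92, difference −14.1 points (95% Newcombe CI −26.5 to −1.2).
- Restricted: 32/64 vs 45/64, difference −20.3 points (−35.7 to −3.4).

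**The case against.** The strongest reply is that the size is entirely assumed. Neither f, s nor a nighttime q appears in the documents, and if few patients enter with a night score below 2 the effect is negligible. That stands, and it is why the point is conditional.

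Next, the plan expects equal efficacy. If nighttime rates, f and s are all equal across arms, the expected difference is zero either way. The 50% vs 70% contrast is only illustrative. With 60% vs 70%, Fisher power is 21.0% (all ITT) against 22.1% (restricted) at f = 10%, and 15.4% against 17.3% at f = 30%, so restriction gains little. In the worked example both analyses reach p < 0.05 (0.048 and 0.030), and the restricted interval is wider. These points limit the dilution argument; they do not answer the overstated rate within each arm.

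Day 8 status in all ITT patients is also a legitimate quantity. It keeps everyone randomised and captures worsening from below 2, so it should be kept. But it is a status, and neither the table's label nor the protocol's description as response fits it.

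Table 9.12 does show Day 1 night scores and their change by arm, but not the count below 2, and any mixed model would concern scores rather than the responder rate. The footnote lets table layouts change but requires their meaning to be kept, so it does not correct the label.

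On the interval, SAP 7.1 lists CIs for a difference in proportions among its general methods, but assigns none to these endpoints.

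**Conclusion.** The concern holds. Followed exactly, the SAP counts patients with no night cough of 2 or more at entry as resolved, and no planned table lets a reader separate them.

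Overstatement in each arm is f·(s − q): at q = 70% and s = 100%, 3 points if f is 10% and 9 points if f is 30%; none if f = 0 or s = q. Since f and s are unknown and q is borrowed from daytime, these figures are a range, not an estimate. The fault is one of labelling and dilution, not a systematic bias towards one arm, because randomisation balances f in expectation.

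The endpoint is secondary. The primary analysis, the sample size and the type I error of the Fisher test are unaffected. It should be corrected, but it does not threaten the trial's main conclusion.

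The missing 95% CI is a direct protocol–SAP mismatch and depends on none of these assumptions.

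**What to change.** 1. In SAP 7.2.4.1 and Table 9.10, report resolution (Day 8 night score below 2) among ITT patients with a Day 1 night score of 2 or more.
2. Keep the all-ITT rate beside it, relabelled as nighttime score below 2, so that worsening from below 2 remains visible.
3. Show the number below 2 at night on Day 1, by arm.
4. For Day 4 (SAP 7.2.4.2 and the shell "Secondary efficacy. Daytime and Nighttime cough resolution"), state whether daytime and nighttime are reported separately or as a composite. Apply the restriction only to a separate nighttime rate; a composite requiring both scores below 2 needs none, because every patient enters with a daytime score of 3 or more.
5. Separately, add the 95% CI of protocol 9.7.2 to SAP 7.2.4.1, 7.2.4.2 and Tables 9.10 and 9.11. Protocol 9.7.2 does not say whether it is per arm or for the difference; the simplest choice is the Levopront minus Libexin difference with a two-sided 95% interval by the Newcombe method already named in SAP 7.2.3.

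The cost is SAP and table wording only, since the night score is already collected at Visit 1. The restricted rate has a smaller denominator and a wider interval: about 64 instead of 92 per arm if f is 30%.
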